1. REVISION HISTORY

Author	Revision	Date	Description of change
[name] [name]	A	04/MAR/2015	First release, this revision of the document is also known as the REV_A_04MAR2015 referenced in the clinical research agreement and insurance agreement.
[name] [name]	B	09/APR/2015	Revisions based on reviewer comments prior to NZ HDEC submission.
[name] [name]	C	30/APR/2015	Revision to spirometry wording and time frame for recruitment
[name] [name] [name]	D	24/AUG/2015	Revisions based on review by [name] (for detail see tracked changes document)
[name] [name] [name]	E	20/NOV/2015	Revisions to oxygen titration methodology, time windows for phone calls and visits, event reporting, point of enrolment and training requirement. The clinical trials registration number has been added. Minor formatting changes to differentiate protocol from F&P internal documents. In addition, [name] is to be made the new PI.

2. LIST OF ABBREVIATIONS

AE	Adverse Event
AECOPD	Acute Exacerbation of Chronic Obstructive Pulmonary Disease
COPD	Chronic Obstructive Pulmonary Disease
CIP	Clinical Investigation Plan
CRF	Case Report Form
ED	Emergency department/Emergency room
FEV1	Forced expiratory volume in 1 second
FVC	Forced Vital Capacity
GP	General Practitioner
IRB	Institutional Review Board
IEC	Independent Ethics Committee
NHF	Nasal High Flow
NZ	New Zealand
PI	Principal Investigator
SAE	Serious Adverse Event
SVC(in)	Slow Vital Capacity (inspiratory)
USA	United States of America

3. MONITORING ARRANGEMENTS AND DATA MANAGEMENT

3.1. Monitoring arrangements

Site/clinical monitoring to assure high quality trial conduct will be conducted by Fisher and Paykel Healthcare or its representative. "On site" monitoring of individual case histories, assessment of adherence to the protocol, ensure the ongoing implementation of appropriate data entry and quality control procedures, and general assessment of adherence to good clinical practices.

The monitor will be allowed, on request, to have access to all source documents needed to verify the entries on the CRF and other protocol-related documents; provided that subject confidentiality is maintained in agreement with international, national and local regulations. It will be the monitor's responsibility to inspect the CRF at regular intervals throughout the study, to verify the adherence to the protocol and the completeness, consistency and accuracy of the data being entered on them.

The investigator's file will contain the protocol/amendments, financial disclosure form, CRFs and data clarification and query forms, HREC approval with correspondence, informed consent, staff curriculum vitae and authorization forms, screening and enrolment logs, and other appropriate documents/correspondence as per ICH/GCP and local regulations.

3.2. Data Management

Both physical and electronic copies of forms will be kept by the sponsor at FPH.

4.5. Other

WHO Universal Trial Number (UTN): U1111-1158-9792
ClinicalTrials.gov Identifier: NCT02552732

6. DEVICE INFORMATION

6.1. Identification of the Medical Device

myAIRVO 2 is a humidifier with integrated flow generator that entrains room air and prescribed medical gases. The device then humidifies these gases through a chamber, which are delivered to the patient via a nasal cannula 'Optiflow+™' via a heated breathing tube, as depicted in figure 1 below. Collectively both the device and the cannula deliver NHF therapy.

[figure not shown]

Figure 1 'myAIRVO 2 and Optiflow+ cannula'

myAIRVO 2 is designed to deliver heated and humidified gas over a range of temperature settings (31°C, 34°C and 37°C) and variable flow rates (10 to 60 L/min). These settings help preserve compliance with the treatment regimen.

6.2. Device Risk Analysis and Management

The AIRVO 2 series devices (including myAIRVO 2) are designed and released to market, in accordance to the FPH design control procedures incorporating a Risk Management File, and governed by the medical device industry Standards:

- ISO-13485:2003 (Quality Systems - Medical Devices - Particular Requirements); and
- ISO-14971:2007 (Application of Risk Management to Medical Devices).

7. JUSTIFICATION FOR A CLINICAL TRIAL

7.1. Synopsis

The aim of this feasibility study is to provide data for a subsequent randomized controlled trial to investigate if patient outcomes will be improved after an acute COPD exacerbation using domiciliary NHF compared to standard care. This feasibility study will investigate the following: process, resources, management and scientific aspects of delivering NHF as an adjunct therapy in COPD patients.

7.2. Literature Review

Chronic obstructive pulmonary disease (COPD) affects around 15% of the adult population of New Zealand, with AECOPD resulting in more than 9,000 hospital admissions per year.¹ The burden of COPD is recognized internationally with high admission and readmission rates reported in the United States of America (USA),² Europe^{3,4} and Australia.⁵

There is increasing interest in the provision of NHF therapy to improve outcomes in patients with COPD. The myAIRVO 2 device is designed to deliver heated and humidified gases to provide respiratory support. Previous research in patients with COPD and bronchiectasis, has demonstrated to significantly reduce exacerbation days and time to first exacerbation, as well as improve lung function and quality of life.⁶

myAIRVO 2 may provide direct benefit to patients recovering from AECOPD by providing airway hydration, improving mucociliary clearance⁷ and increasing nasal temperature (to 37°C) which may reduce the risk of subsequent infection.⁸ As well as improving clinical outcomes, NHF therapy may reduce readmission rates conferring significant economic benefits. In the USA, 21% of admissions to hospital with AECOPD are followed by readmission within 30 days, and the costs of a second hospital stay are consistently higher when compared with the original admission.² The proportion of patients that are readmitted within 30 days with a primary diagnosis of AECOPD in the USA is 7%.² This is similar to New Zealand data, where 8% of patients are readmitted with a primary diagnosis of AECOPD within 30 days of discharge, and 14% within 60 days (based on recent Wellington Regional Hospital audit data).⁹

In preparation for a randomized controlled trial powered to detect change in readmission rates, this study will inform an appropriate myAIRVO 2 prescription for COPD patients, recruitment rate projection and aspects of the trial design that need to be changed to increase the quality of data collection and patient compliance.

Should NHF therapy be demonstrated as an effective and well tolerated intervention to reduce hospital readmissions and improve symptoms following AECOPD, NHF therapy could be considered an effective and routine treatment option on discharge.

7.3. Preclinical Testing

Appropriate pre-clinical testing and data evaluation was carried out as a part of the product release for the AIRVO 2 series. The AIRVO 2 series is cleared for both hospital and home use by the FDA, and as this study only involves unmodified devices used as per intended use, further preclinical/safety testing is not required for this feasibility study.

7.4. Previous Clinical Experience

The AIRVO 2 series has been and is currently used for delivering NHF therapy to COPD patients, worldwide (including New Zealand and USA), in health care and domiciliary settings since 2013.

7.5. Justification for Administration

Participants will be asked to use myAIRVO 2, for participants on domiciliary oxygen, the oxygen will be delivered via the device (see section 9.10.04). Participants will not be given a specific time period to wear the device, but encouraged to use the therapy every day as much as possible without impacting on their daily routines. The first day after discharge will be classed as day one of the study. NHF therapy will be monitored from day one for a period of 30 days.

For all participants NHF therapy will be initiated at 25L/min with a the temperature setting of 37°C. All participants have the ability to reduce the temperature setting to 34°C. In participants who are not prescribed oxygen there will be the further option to increase or decrease flow rates (up to 30L/min or down to 20L/min). These modifications are to assist with comfort and adherence. Patients who are prescribed domiciliary oxygen flow rates will remain constant to deliver a more consistent concentration of oxygen.

The outcomes of this study will inform the appropriate methodology for subsequent randomized control trials to investigate the efficacy of NHF therapy in the long-term management of COPD patients. Given this, therapy settings, compliance to the therapy in this feasibility study are modifiable to gain maximum understanding of therapy usage.

8. OBJECTIVES OF THE CLINICAL INVESTIGATION

8.1. Hypothesis

This is a feasibility study to assess the process, resources, management and scientific aspects of NHF therapy use following discharge from hospital post AECOPD. This will inform the randomized controlled trial design to ensure methodological robustness.

8.2. Objectives

The objectives of the study:

1. To estimate the duration of use of the device including the mean hours of use per day and number of days use, to inform an daily myAIRVO 2 prescription for the proposed randomized controlled trial
2. To estimate the proportions of potential participants who could proceed to the proposed randomized controlled trial
3. To estimate the proportions of potential participants who would require oxygen delivery through myAIRVO 2 in the proposed randomized controlled trial
4. To estimate aspects of the use of myAIRVO 2 after discharge and to in particular estimate patient ratings of ease of use, and the proportion of those who required changes to initial settings of temperature and flow, and the magnitude of these changes, to inform prescription design for the proposed randomized controlled trial
5. To estimate particular clinical outcomes relevant to the planned randomized controlled trial, including hospital readmission, Emergency Department (ED visit) and General Practitioner (GP) visit rates.

8.3. Population

One hundred patients admitted to hospital with an AECOPD. Participants will be recruited from two sites: Wellington Regional Hospital, New Zealand (20 participants) and Alana Healthcare, USA (80 participants). Please see section 9.8 for details of inclusion/exclusion criteria.

8.4. Risks & Benefits

NHF therapy delivered by myAIRVO 2 may provide direct benefit to patients recovering from AECOPD by providing overnight respiratory support, improvement in mucocilliary clearance⁷ and increased nasal temperature (to 37°C) which may reduce the incidence of subsequent infection.⁸

myAIRVO 2 operates according to the principle of all active respiratory gas humidifiers by artificially conditioning inspiratory airflow with heat and humidity.

The risk of using an active humidifier are electric shocks, burns of the patient and tubing melt down. The risks stated above are associated with any medical device, which uses electrical power for heating/warming. These risks are minimized as myAIRVO 2 is CE marked and has FDA Premarket Approval (PMA) clearance. The use of the device is in accordance to the user instructions and participants will be instructed according to the user guide.

The risks of NHF therapy for patients who receive supplemental oxygen are inappropriate oxygen delivery, with the potential for hyperoxemia, carbon dioxide retention, or hypoxemia. These risks will be minimized by an initial oxygen assessment by the study physician, comprehensive education for participants and exclusion of participants who the investigator is concerned may be at risk of giving themselves incorrect oxygen delivery.

There is no contraindication known to the use of active humidifiers in patients.

8.5. Essential Requirements of the Relevant Directive

ICH GCP and Ethics Committee approval.

9. CLINICAL INVESTIGATION DESIGN

9.1. Type of Investigation

Feasibility study.

9.2. Controls

There is no control group required for this study.

9.3. Bias

The feasibility study is designed to inform a future randomized controlled trial. Therefore bias is not relevant for the outcomes of this study.

9.4. End Points

The following end points will be evaluated:

Primary outcome:

The primary outcome will be NHF use for 30 days following discharge after AECOPD. Use will be expressed as hours of myAIRVO 2 use per day over 30 days, as obtained by myAIRVO 2 electronic monitoring.

Secondary outcomes:

Other use variables:

- i. Number of days of use, adjusted for number of days with myAIRVO 2 at home
- ii. Average use per day of myAIRVO 2 during week 1, week 2, week 3 and week 4.
- iii. Average use per day on days of myAIRVO 2 use

Withdrawals and exclusions:

- i. Proportion of participants screened that were excluded
- ii. Reason for exclusion
- iii. Proportion of participants enrolled that were withdrawn
- iv. Reason for withdrawal

Participants requiring oxygen delivery via myAIRVO 2:

- i. Proportion of participants using domiciliary oxygen

Aspects of myAIRVO 2 use:

- i. Proportion of participants who reported having reduced myAIRVO 2 flow settings from the initial flow
- ii. Reduction in flow
- iii. Proportion of participants who reported having increased myAIRVO 2 flow settings from the initial flow
- iv. Increase in flow
- v. Proportion of participants who reported having reduced myAIRVO 2 temperature setting from the initial setting
- vi. NHF therapy Questionnaire results

Clinical outcomes

- i. Proportion of participants with at least one hospital readmission within 30 days of discharge
- ii. Reasons for hospital admissions (AECOPD, other respiratory cause or other cause)
- iii. In those that had at least one hospital readmission:
 - a. Number of readmissions
 - b. Time to first hospital readmission
 - c. Hospital readmission length
- iv. Proportion of participants with at least one ED visit within 30 days of discharge
- v. Reason for ED visits (AECOPD, other respiratory cause or other cause)
- vi. In those that had at least one ED visit:
- vii. Number of ED visits
- viii. Time to first ED visit
- ix. Proportion of participants with at least one GP visit within 30 days of discharge
- x. Reason for GP visits (AECOPD, other respiratory cause or other cause)
- xi. In those that had at least 1 GP visit within 30 days of discharge: number of GP visits
- xii. LACE Index for hospital admissions
- xiii. Lung function measurements (FEV₁, SVC_{in} and FVC) at day 1 and 31.

* An ED visit is counted if the patient went to ED for assessment and was not subsequently admitted to a hospital ward.

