9.10.2. Interventions

a. Participants will be split into 2 groups (those on a domiciliary oxygen prescription at the time of study entry and those who are not) with both groups receiving NHF therapy by myAIRVO 2. Participants will be encouraged to use myAIRVO 2 as much as possible (day and night) each day without impacting on daily living activities. Participants who are prescribed domiciliary oxygen will use NHF therapy via myAIRVO 2 with supplemental oxygen delivered via the device (section 9.10.04).

b. Interventions will be initiated from the time the participant is enrolled in hospital, to aid familiarization and acclimatization, and used until 30 days following discharge. Note the day of discharge is defined as Day 0.

c. By default, NHF will be set at 25L/min at 37°C. However, all participants are able to lower the delivered temperature to 34°C. For participants without a domiciliary oxygen prescription they can also increase/decrease the flow rate (up to 30L/min or down to 20L/min). Participants who have domiciliary oxygen flow rates are fixed in order to deliver a more consistent concentration of oxygen to maintain oxygen saturation.

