9.10.4. Post-discharge methods

- a.** A home visit will be made by an investigator on the day of or day after discharge. The investigator will:
- i. Ensure the equipment is set up correctly and reinforce the previous training on myAIRVO 2. (Appendix 1).
 - ii. Check participants will have the myAIRVO 2 user manual and the 'Patient summary sheet' as an easy reference for device use.
 - iii. Perform lung function tests using a spirometer (Jaegar pneumotac spirometer with J-Lab software) according to ATS/ERS Taskforce standards.^{10 11} Participants will not be required to withhold bronchodilator medication prior to testing. The drug, dose and time of the last administration prior to spirometry will be recorded. This will inform COPD severity of participants and baseline lung function measurements.
- b.** Participants on domiciliary oxygen will have oxygen saturations recorded on simple nasal prongs according to their existing prescription. NHF therapy will then be initiated and oxygen will be titrated through myAIRVO 2 to determine the flow of oxygen delivery required to achieve the same oxygen saturation level (Section 9.10.04).

c. myAIRVO 2 devices will electronically record data on the date and time the device was used. Should participants change the flow of their myAIRVO 2 device (participants without domiciliary oxygen only) or alter the temperature, they will be asked to document this in their diary.

d. On the 3rd, 7th, 14th and 21st and 28th day post discharge the investigator will contact the participant by phone. Participants will be asked:

- i. If they are having any problems using myAIRVO 2.
- ii. If they have needed to return to the hospital, the reason and length of their hospital visit. These details will be checked against hospital records. In addition, they will be asked if they have needed to visit their GP or other allied health care practitioners and the reason. The Investigator will complete the CRF and the medical history log, concomitant medications log, medical contact log, adverse event/ serious adverse event forms as required.

e. On the 31st day post discharge an investigator will perform a home visit or the participant will visit the study investigator at their clinic office.

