11. STATISTICAL CONSIDERATIONS

11.1. Description of the Statistical Design

As this is a feasibility study the primary outcome variable (9.4.1) will be expressed as the mean number of hours per day used, with standard deviation. The mean may be weighted for time in the study and allocated 95% confidence intervals for each by weighted regression.

Continuous outcomes 9.4.2-4, 9.4.11, 9.4.13, 9.4.18c, and 9.4.26 will also be expressed as mean, standard deviation. Means may be weighted for time in the study and allocated 95% confidence intervals for each by weighted regression.

For the mean number of hospital readmissions (9.4.18a), ED visits (9.4.21a) and GP visits (9.4.24) Poisson regression will be used.

Time to first hospital readmission (9.4.18b) and first ED visit (9.4.21b) will be analyzed by Kaplan-Meier survival estimates and CI for quantiles of survival, those who don't get admitted within the study time will be censored data.

Categorical outcomes 9.4.5-10, 9.4.12, 9.4.14, 9.4.16, 9.4.17, 9.4.19, 9.4.20, 9.4.22, 9.4.23 and 9.4.25 will be described by absolute numbers and proportions. Confidence intervals may be calculated for outcomes 9.4.5-10, 9.4.12, 9.4.14, 9.4.16, 9.4.19, and 9.4.22.

NHF questionnaire results (9.4.15) will likely be presented by mean, standard deviation and confidence interval, however if the data distribution is heavily skewed data may be presented as proportions.

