11.6. Selection Criteria

For endpoint details see section 9.4. All participants who were screened to take part in the study will be included in the analysis of endpoint 2.b.i. All patients who were discharged with a myAIRVO 2 device to take home will be included in analysis of all other endpoints.

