16. APPENDIX 1: FLOWCHART

17. APPENDIX 2: TRAINING SESSION REQUIREMENTS

Hospital Acclimatization/Familiarization session

Instruction	myAIRVO 2 manual reference
Familiarize and acclimatize participant to NHF therapy using myAIRVO 2, this should include a period of NHF use by the participant.	N/A
Explain warnings on page A-2 of myAIRVO 2	A-2
Explain how myAIRVO 2 works and what each of the consumables are for	A-3
Demonstrate switch on and startup of myAIRVO 2 and document participant's nasal cannula size (small, medium or large)	A-7
Instruct participant to change temperature setting and NOT activate junior mode	A-8 to A-9
Participants NOT on domiciliary oxygen: Demonstrate how to change target flow OR Participants on domiciliary oxygen only: Demonstrate how to connect oxygen tubing, explaining warnings for oxygen use & instruct participant NOT to change myAIRVO 2 flow setting	A-8 A-10
Demonstrate how to put myAIRVO on night mode	A-9
Give participant myAIRVO 2 manual and 'Quick guide' sheet	N/A

Full training Session at home visit:

Instruction	myAIRVO 2 manual reference
Explain warnings on page A-2 of myAIRVO 2	A-2
Re-explain how myAIRVO 2 works and what each of the consumables are for	A-3
Demonstrate startup of myAIRVO 2 including: 
 - Position of AIRVO - Water chamber instillation, and that distilled water must be used - How to check water level and to avoid letting water run out - Installation of heated breathing tube 	A-4 to A-6
Demonstrate how to switch on myAIRVO 2 including: 
 - Switch on - Warm up screen - Connection of patient interface 	A-7
Explain the drying mode and that should the participant wish to use myAIRVO 2 while it is in drying mode they can override it by pressing the main button twice or switching it off then on at the wall.	A-7
Participants NOT on domiciliary oxygen: Demonstrate how to change target flow OR Participants on domiciliary oxygen only: Demonstrate how to connect oxygen tubing, explaining warnings for oxygen use & instruct participant NOT to change MyAIRVO 2 flow setting	A-8 A-10
Instruct participant NOT to activate junior mode	A-8 to A-9
Demonstrate how to put myAIRVO 2 on night mode	A-9
Show participant where the alarms section is in the manual is and advise to: 
 - Consider contact with investigator if the 	A-11 to A-12

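### The two flow-change proportions count oxygen users, whose flow is fixed, in the denominator, so they understate how often participants allowed to adjust flow did so

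*Combined protocol and SAP*

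**What the plan says.** Section 9.4 lists, under aspects of device use, the "Proportion of participants who reported having reduced myAIRVO 2 flow settings from the initial flow", a parallel item for increased flow, and the size of each change. Section 11.1 refers to endpoints by a running number. Counting the 9.4 items in order (primary 1, other use variables 2 to 4, withdrawals and exclusions 5 to 8, oxygen 9, aspects of use 10 to 15) makes flow reduced 9.4.10 and flow increased 9.4.12, with their sizes 9.4.11 and 9.4.13. This fits 11.1, which treats 10 and 12 as categorical and 11 and 13 as continuous. The categorical outcomes "will be described by absolute numbers and proportions", with confidence intervals optional for 9.4.10 and 9.4.12.

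The analysis set is in section 11.6: "All patients who were discharged with a myAIRVO 2 device to take home will be included in analysis of all other endpoints". The only exception is the screening endpoint.

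Three places treat oxygen users differently on flow:

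- Section 9.10.2(c): "Participants who have domiciliary oxygen flow rates are fixed in order to deliver a more consistent concentration of oxygen". Section 7.5 says the same.
- Appendix 2, for participants on domiciliary oxygen: "instruct participant NOT to change myAIRVO 2 flow setting".
- Section 9.10.4(c), the diary instruction: "Should participants change the flow of their myAIRVO 2 device (participants without domiciliary oxygen only) or alter the temperature", followed by the request to write the change down.

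Objective 4 in section 8.2 wants "the proportion of those who required changes to initial settings of temperature and flow, and the magnitude of these changes", as input to the prescription for the planned randomised trial.

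**The concern.** A proportion is informative about a behaviour only if the people in its denominator could have shown it. Here one group is barred from the behaviour by protocol and is not asked to record it, but is counted all the same. The result blends two quantities that the study sets out to estimate separately: how often participants with the option adjust flow (objective 4), and what share of participants are on oxygen (objective 3). A trial with a different oxygen mix could not use the blended figure directly.

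The plan does write out a subset where it wants one. The readmission details open with "In those that had at least one hospital readmission", and the ED and GP items have similar clauses. The flow items have none. The limit to non-oxygen participants that applies when data are collected is not carried into 9.4 or section 11, and although 9.10.2(a) splits participants by oxygen status, section 11 plans no analysis by that split.

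**Working it through.** **The plan's own figure.** Section 11.2 gives 100 participants from a minimum of 80 and 20% drop-out: 80 / (1 − 0.20) = 100. This reproduces and is not affected by the present point.

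**Inputs.** Let *p* be the proportion changing flow in a given direction among those allowed to, and *f* the share of device users on domiciliary oxygen. The documents give neither; *f* is itself endpoint 9.4.9. Both are therefore assumed: *p* from 20% to 40%, *f* from 10% to 50%.

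**Formula.** If oxygen users adhere, they contribute no events:

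- reported proportion = *p* × (1 − *f*)
- gap = *p* × *f*
- gap relative to *p* = *f*, whatever *p* is

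**Reported proportion, with the gap in percentage points in brackets:**

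| *p* | *f* = 10% | 20% | 30% | 40% | 50% |
|---|---|---|---|---|---|
| 20% | 18% (2) | 16% (4) | 14% (6) | 12% (8) | 10% (10) |
| 30% | 27% (3) | 24% (6) | 21% (9) | 18% (12) | 15% (15) |
| 40% | 36% (4) | 32% (8) | 28% (12) | 24% (16) | 20% (20) |

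**Examples with Wilson 95% intervals.** The interval has centre (x + z²/2) / (n + z²) and half-width z / (n + z²) × √(x(n − x)/n + z²/4), with z = 1.96. Take 80 as the number discharged with a device (an assumption; 11.2 gives 80 as the minimum needed).

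- 24 on oxygen (*f* = 30%), so 80 − 24 = 56 may adjust, and 22 report the change. As written: 22/80 = 27.5% (18.9 to 38.1). Among those allowed: 22/56 = 39.3% (27.6 to 52.4). The as-written interval lies wholly below 39.3%.
- 8 on oxygen (*f* = 10%), so 72 may adjust, and 29 report the change. As written: 29/80 = 36.25% (26.6 to 47.2). Among those allowed: 29/72 = 40.3% (29.7 to 51.8). The difference is small.

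With all 100 participants, *p* = 40% and *f* = 30%, the figures are 28/100 = 28% (20.1 to 37.5) against 28/70 = 40% (29.3 to 51.7).

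**Related endpoints.** For 9.4.11 and 9.4.13 (size of change) no denominator is stated. If non-changers were entered as zero, the means would be diluted too. The temperature endpoint 9.4.14 is unaffected, because every participant may lower the temperature.

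**The case against.** The strongest reply is that the text need not be read this way. The endpoint counts those who reported a change, the diary instruction on flow is limited to non-oxygen participants, and section 9.10.7 lists separate diaries for the two groups. On that view oxygen users have no value for this item, rather than a zero. Nor can 11.6 literally fix every denominator, since 9.4 contains items limited to readmitted patients and one based on those enrolled. This reading is possible, but neither 9.4 nor section 11 states it, and 11.6 read plainly says otherwise. The diaries, questionnaire and data collection SOP are listed but not shown, so they cannot settle it. They would not alter the fixed-flow rule in any case.

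A second reply is that objective 4 does not restrict itself to those allowed to adjust, and that oxygen users are expected in the randomised trial, so an all-participant figure has some planning value. That is fair, and it supports keeping the figure as a supplement. For prescription design, the rate among those with the option is the more useful one.

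A third reply is that little is lost. Section 11.1 requires absolute numbers, including the oxygen count, so under full adherence the restricted rate and its interval follow exactly from what is reported. There are no pass/fail criteria (11.3). All of this stands. But recovery fails if some oxygen users change flow despite instruction, because counts by oxygen group are not planned.

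Finally, the size is assumed throughout. No oxygen share is given, and excluding patients with a new oxygen prescription (9.8) may keep it low. The upper end of the range should not be taken as expected. On 9.4.11 and 9.4.13, a summary among changers is already the natural reading; stating it only removes doubt.

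**Conclusion.** The concern holds. Applied as written, 11.6 gives flow-change proportions that fall below the rate among participants free to adjust, by a relative amount equal to the oxygen share. Over the assumed ranges this is 2 to 20 percentage points: minor if about one in ten is on oxygen, and large enough in the 30% example to put the relevant estimate outside the reported interval. The result rests on oxygen users following the fixed-flow instruction and on the assumed values of the change rate, the oxygen share and the number discharged with a device. No test or decision threshold depends on these endpoints and no data are lost. It should be corrected because the estimate is meant to feed the next trial's prescription and the correction is simple. It does not threaten the study.

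**What to change.** Add a sentence to 11.6, with a matching clause in 9.4, stating that:

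- 9.4.10 and 9.4.12 use as denominator the participants discharged with a device and without a domiciliary oxygen prescription;
- the all-participant figure is given at most as a supplement, with any flow change known to have been made by an oxygen user counted separately;
- 9.4.11 and 9.4.13 are summarised among those who made the change in question;
- 9.4.14 keeps all participants discharged with a device.

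Oxygen status is already recorded at the pre-discharge assessment (9.10.3), so no new data are needed. The price is precision: in the 30% example the denominator falls from 80 to 56 and the half-width of the 95% interval rises from (38.1 − 18.9)/2 = 9.6 to (52.4 − 27.6)/2 = 12.4 percentage points.
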